10.4 Exclusion criteria

To participate, the women must not meet any of the exclusion criteria listed below at entry of the study nor under time of treatment.

[figure not shown]
Criteria related to study design

- Any previous or current diagnosis of breast cancer (including carcinoma *in situ*).
- Any previous diagnosis of cancer with the exception of non-melanoma skin cancer and *in situ* cancer of the cervix.
- A history of major surgery of the breast, e.g., reduction or enlargement, which might affect density measurements.
- Mammographic BI-RADS *malignancy* code 3, or above, at baseline mammography, or at mammography during time of treatment. Recall for additional examinations due to technical problems with the mammogram is accepted.
- Currently using estrogen and progesterone based hormone replacement therapy (oral or patches). Local estrogen treatment is accepted (ex. Vagifem).
- Non-medical approved drugs against hot-flashes including phytoestrogen.

Criteria related to safety

- A history of thromboembolic disease such as embolus, deep vein thrombosis, stroke, TIA or myocardial infarction.
- Known APC (Activated Protein C)-resistance, an inherited haemostatic disorder.
- Women who have an increased risk of venous thrombosis due to immobilization, e.g., using wheelchair.
- Known uncontrolled diabetes.
- Hypertension at baseline, defined as systolic pressure higher than 140 mm Hg and diastolic higher than 90 mm Hg
- Prescribed and regular use of anticoagulants (defined as substances included in group B01A in the ATC-system)
- Not able to understand the study information and/or informed consent.

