5.5 Mammographic density

In a conventional breast cancer prevention study the outcome would be number of breast cancers in each arm given a predefined time period. Such a study requires a long follow-up and a very large

number of participants. An alternative is to use mammographic density change as a proxy for therapy response.

Mammographic density is the white part of the mammogram and consist of glandular and connective tissue. The black, non-radiolucent part is fat. The more glandular and more connective tissues, the whiter the breast, and thus, the higher the risk of breast cancer [Boyd, 2007]. Factors that influence risk of breast cancer are known to influence density. Hormone replacement therapy increases density and risk of breast cancer [Brand, 2013], while tamoxifen has the opposite effect [Li, 2013].

In addition to be a excellent marker of risk, mammographic density has been shown to be a reliable proxy for therapy response. Mammographic density has been assessed in a nested case-control study within the IBIS-1 study, a randomised prevention study of tamoxifen vs. placebo. The density decrease, over the first 18 months, in 123 women diagnosed with breast cancer, was compared to 942 women without breast cancer [Cuzick, 2011]. Forty-eight per cent of the women treated with tamoxifen experienced a 10% or greater reduction in breast density and had a 63% reduction in breast cancer risk compared to women in the placebo group. In contrast, those who took tamoxifen but experienced less than a 10% reduction in breast density had no risk reduction.

Within the Karma group a parallel study was conducted including breast cancer patients who were treated with adjuvant tamoxifen therapy [Li, 2013]. Forty-eight per cent of the women experienced a decrease in density of > 20 % over a 12 month period and had a reduced breast cancer recurrence of 50%. These findings are fully supported by a very recent finding by a US group [Nyante, 2015].

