5.6 Study duration

The Karisma-1 pilot trial (Eudra CT2014-005-005-20) preceded the Karisma-2 trial. The major focus of the pilot trial was to estimate time to mammographic density change. In all, 32 healthy women completed the 6 month trial and were exposed to 10 or 20 mg/day of oral tamoxifen.

The results of the Karisma-1 trial showed a mammographic density decrease after the full study period of 6 months, of about 50% for one quarter of the participants. For another quarter of the participants

a \approx 20% mammographic density decrease was seen. The remaining 50% of the participants did not experience any change in mammographic density.

Table 1 displays the change in mammographic density among the 32 patients seen after 3, 6 and 9 month of follow up. The biggest decrease is seen the first 3 months and the decrease continues even after the treatment was stopped at 6 months.

Table 1. Mean percent dense area and density change from baseline in percent in the Karisma-1 pilot study (n=32), in relation to months in study.

	0 month	3 months	6 months	9 months
Mean % dense area	17.6	15.8	15.3	14.6
Mean % change from baseline	-	-1.8	-2.3	-3.0

The results of the Karisma-1 pilot trial show that 3 months of oral tamoxifen exposure is enough to significantly influence mammographic density. Since it could be that the uptake of topical endoxifen, in contrast to oral tamoxifen, is slower, the treatment period in Karma CREME-1 trial has been set to 6 months, with mammograms and density measurements performed at 3 and 6 months.

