10.3 Inclusion criteria

To participate, the women must meet the following inclusion criteria:

- Attending the national mammography screening program, i.e., aged 40-74 and have performed a screening mammogram maximum 3 months prior to study inclusion
- Mammographic density $\geq 4.5\%$ density (volumetric) measured by Volpara, at the screening mammogram performed in connection to baseline (maximum 3 months prior to inclusion). The threshold value of 4.5% corresponds to the clinically used BI-RADS score A
- Postmenopausal, defined as no period of menstruation during last 12 months independent of any hormonal treatment
- Informed consent must be signed before any study specific assessments are performed

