10.7.9 Prior and concomitant therapy

All concomitant therapy must be recorded in the eCRF. No other drug under investigation may be used concomitantly with the study medication.

Although endoxifen is one of the first pass metabolites of tamoxifen, conditions that require medications metabolized by the P450 pathway should be carefully monitored during this study.

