10.7.10 Prohibited medications

- Estrogen and progesterone based hormone replacement therapy (other than local), are not allowed during the study or used at study enrolment. Rationale for prohibition is potential interference with outcome measurements.
- Prescribed and regular use of anticoagulants (defined as substances included in group B01A in the ATC-system) are not allowed during the study or at time of study enrolment. Prescription of anticoagulants indicates that person is at risk of thrombosis. The literature and tamoxifen product information also describe concomitant use of tamoxifen and warfarin as a contraindication, since this combination may result in an increase in the anticoagulation and the risk of bleeding complications. Since the exact mechanism triggering this effect is not clear, the Sponsor declares the same precautions regarding endoxifen.
- Non-medical approved drugs against hot-flushes including phytoestrogen are not allowed during the study or used at study enrolment. Rationale for prohibition is potential interference with outcome measurements.

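### Density-altering drugs are barred at enrolment and during treatment, but not at the baseline mammogram, which may be up to 3 months older

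*Combined protocol and SAP*

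**What the plan says.** **Drug rules.** Section 10.4 states that participants "must not meet any of the exclusion criteria listed below at entry of the study nor under time of treatment". The HRT item reads "Currently using estrogen and progesterone based hormone replacement therapy (oral or patches"), with local estrogen accepted. Section 10.7.10 adds "Estrogen and progesterone based hormone replacement therapy (other than local), are not allowed during the study or used at study enrolment", and for herbal products "Non-medical approved drugs against hot-flushes including phytoestrogen are not allowed during the study or used at study enrolment". The reason it gives for both is possible interference with the outcome. No section gives a look-back or washout period. Tamoxifen and other selective estrogen receptor modulators (SERMs) appear in neither list. The nearest rule is in 10.7.9: "No other drug under investigation may be used concomitantly with the study medication".

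**Baseline image.** Section 10.3 requires that women "have performed a screening mammogram maximum 3 months prior to study inclusion". Appendix A takes the month-0 mammogram from routine screening, and 10.5.3 adds no new image. Section 8.1.1 defines the primary endpoint as individual change from that image, and in a parenthesis equates study entry with the screening mammogram.

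**Effect on density.** Section 5.5 says "Hormone replacement therapy increases density and risk of breast cancer" and that tamoxifen does the opposite. Section 5.6 reports, for oral tamoxifen, that "the decrease continues even after the treatment was stopped at 6 months".

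**The concern.** The drug rules protect the two follow-up images but not the image they are compared with. If a woman's baseline image was taken on HRT and her month-3 and month-6 images off it, part of her fall comes from stopping HRT. It would still be recorded as change on study, in whichever arm she joins. The menopausal criterion in 10.3 does not remove such women, because it applies regardless of hormonal treatment.

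The same holds for a woman who takes and stops oral tamoxifen between the image and inclusion. Karisma-2 invites screening attendees at the same hospital (5.1) and recruits to December 2018 (section 4), overlapping CREME-1 inclusion from April to, at latest, September 2018 (13.1).

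Three things are at stake: the individual-level endpoint, the density change that each participant will be told (10.5.6), and the rule to proceed if mt-mc exceeds 0% (9.1.3) with 30 women per arm.

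**Working it through.** **1. Timing.** Visits are counted from baseline (10.5.5, 10.5.6). With an image up to 3 months older, the measured changes can span up to 3 + 3 = 6 and 3 + 6 = 9 months, plus the 2-week window. Up to 3 of those months precede study drug.

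**2. Is the woman eligible?**
- 10.3 separates the mammogram from *inclusion*.
- 10.4 tests current use at *entry* and during treatment.
- 10.7.10 tests use at *enrolment* and during the study.
- 10.5.2 and 10.5.3 check eligibility at the Study Centre.

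On these, a woman who stopped HRT after the image passes. Only the 8.1.1 parenthesis, read into the word *entry* in 10.4, would exclude her.

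**3. Standard error of mt-mc.** The plan gives no standard error, so I solved it from Table 5. I read the first column as the 0% effect, because the caption says null although the printed headers repeat those of Table 4. I took the thresholds as absolute density points. With SE = c / z(1-p):
- c = 1, p = 0.24: SE = 1.42
- c = 2, p = 0.08: SE = 1.42
- c = 3, p = 0.02: SE = 1.46

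As a check, SE = 1.42 returns 50%, 24%, 8% and 2% against the printed 50%, 24%, 8% and 2%.

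**4. Shift in mt-mc.** The documents give no size for the HRT effect and no number of affected women. I assume k = 1 to 3 women, each falling d = 2 to 6 points for a non-trial reason. If all are on placebo, mt-mc drops by kd/30. If all are on active drug, it rises by kd/60. With no drug effect, P(go) = Phi(shift / 1.42).

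| Affected women | Shift | P(go), no effect |
|---|---|---|
| None | 0 | 50% |
| 1 x 2 points, placebo | -2/30 = -0.07 | 48% |
| 3 x 6 points, placebo | -18/30 = -0.60 | 34% |
| 1 x 2 points, active | +2/60 = +0.03 | 51% |
| 3 x 6 points, active | +18/60 = +0.30 | 58% |

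Sensitivity: three women falling 5 to 10 points each give 36% to 24% if all are on placebo and 57% to 64% if all are on active drug.

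**5. How extreme is that clustering?** With 30 placebo and 60 active places, three affected women all land on placebo with probability (30 x 29 x 28)/(90 x 89 x 88) = 3.5%, and all on active drug with probability (60 x 59 x 58)/(90 x 89 x 88) = 29%.

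**6. Added noise averaged over allocations.** Let a share q of women be affected. Then SE^2 = 1.42^2 + q(1-q) x d^2 x (1/60 + 1/30). With q = 3/90 and d = 6, this is 2.016 + 0.0322 x 36 x 0.05 = 2.074, so SE rises from 1.42 to 1.44.

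**7. Individual level.** A normal fit to the 12% column of Table 4 gives a mean treatment effect of about 2.3 points. Table 1 shows falls on oral tamoxifen of 1.8 points at 3 months and 2.3 at 6 months. One woman's tamoxifen-sized fall can therefore be about as large as the whole expected effect.

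**The case against.** **The text may already exclude her.** Read together, 8.1.1 and 10.4 would test HRT use on the mammogram date. This stands as a possible reading, so the plan is ambiguous and does not plainly permit such women. It does not close the gap, because 10.3 and 10.7.10 use other time points and eligibility is checked at the Centre.

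**The gap will usually be short.** The Centre visit is linked to the screening examination (10.5.1), and a woman who fails is told why and logged as a non-participant (10.5.2). No section provides for her to stop a drug and return. This limits how often the case arises. But 10.6 bars re-entry only for withdrawn participants, and 10.3 allows the full 3 months.

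**The Karisma-2 route is improbable.** It needs one mammogram to serve two trials, with entry, treatment, withdrawal and CREME-1 inclusion within 3 months. The 16% who left Karisma-2 for side effects (6.3.2.1) is a figure to date, not for the first weeks. The cancer-history exclusions remove most therapeutic users, and section 4 calls preventive use rare. All of this stands; the route is open, but likely to be rare.

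**Stronger readings that the documents do not support.**
- A reader might infer a biased treatment contrast. Randomisation and blinding rule out expected bias.
- A reader might apply the 0.6-point shift to the active mean as well and get a P(go) of 66%. That needs 0.6 x 60 = 36 points, or six women at 6 points each. Three women give at most 0.3 points and 58%.
- A reader might infer that endoxifen left from oral tamoxifen would distort the plasma analysis. The first assay is at month 3, and the documents give no elimination data.

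**Conclusion.** The concern holds as a gap in the eligibility wording. On 10.3, 10.4 and 10.7.10, a woman whose baseline image was taken on HRT or a phytoestrogen product can be included once she has stopped, and her fall is then counted as change on study. Previous SERM use between image and inclusion is not excluded either. The one contrary phrase, in 8.1.1, leaves the point ambiguous.

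The effect on the decision rule is modest and can go either way. Under no drug effect, P(go) moves from 50% to between 48% and 34% if all affected women are on placebo, or to between 51% and 58% if all are on active drug. Averaged over allocations, the added noise is slight. These figures rest on the reading of Table 5 in step 3, a normal approximation, and the assumed one to three women falling 2 to 6 points each. The documents do not show how many women would be affected. The clearer harm is to individual change, which is the stated primary endpoint and is reported back to participants.

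**What to change.** - In 10.4 and 10.7.10, state that systemic HRT, phytoestrogen hot-flush products and SERMs, including Karisma treatment, must not have been in use at the baseline mammogram or between it and randomisation. Any look-back before the image is for the sponsor to set; the documents do not support a particular length.
- Record stop dates for these drugs, so that affected women can be identified in a sensitivity analysis.
- Reconcile *study entry* (8.1.1, 10.4), *inclusion* (10.3) and *enrolment* (10.7.10).
- Reconcile the route wording. The 10.4 item names only oral and patch HRT, while 10.7.10 bars everything except local use, so a user of another systemic route passes the first and breaks the second.

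The cost is a few lines of text, one screening question, and a few women lost to recruitment.

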Healthy post-menopausal women participating in mammographic screening program at SöS Bröstcentrum with a measurable mammographic density, i.e., $\geq 4.5\%$ density (volumetric) measured by Volpara. No history of coagulopathies, cardio-vascular disorders and cancer.

Duration of treatment

6 months

Duration of participants involvement in the study

6 months of exposure to active compound or placebo

Efficacy assessments

Mammographic density after 3 and 6 months.

Safety assessments

The safety profile of each individual and dose group will be determined by clinical assessment, laboratory findings and participant reports. Laboratory findings and AEs will be followed throughout the study period. A Data and Safety Monitoring Board will provide safety oversight of the study.

Statistical methods

Karma CREME-1, is a pilot study conducted to aid the design of a larger future trial. As such, the pilot study is not powered to show statistical significant reductions in breast density in the treatment arms compared to the control arm. Rather, results of the pilot study will be qualitatively presented and assessed, which will aid in making decisions about dosing, study length, and sample size for the larger trial.

Efficacy: Assess change in mammographic density from baseline to 3 and 6 months and from 3 to 6 months of study drug administration.

Tolerability: Assess the grade, severity and frequency of side effects

Safety: rank adverse events by severity, grade, interventions, and resolution.

Table of Contents

PROTOCOL REVISION HISTORY	2
PROTOCOL SYNOPSIS	3
1 LIST OF ABBREVIATIONS AND DEFINITION OF TERMS	8
2 ETHICS	9
2.1 ETHICAL AND REGULATORY REVIEW	9
2.2 ETHICAL CONDUCT OF THE STUDY	9
2.3 PARTICIPANT INFORMATION AND CONSENT	9
2.4 PARTICIPANT DATA PROTECTION	9
3 ADMINISTRATIVE STRUCTURE	10
4 INTRODUCTION	11
5 STUDY RATIONALE	11
5.1 BACKGROUND	11
5.2 TOPICAL ADMINISTRATION RATIONALE	12
5.3 ENDOXIFEN RATIONALE	12
5.3.1 TOPICAL ENDOXIFEN - PHASE 1 DATA	12
5.3.2 PLASMA ENDOXIFEN LEVELS AFTER EXPOSURE TO ORAL TAMOXIFEN	12
5.4 DOSING RATIONALE	13
5.5 MAMMOGRAPHIC DENSITY	13
5.6 STUDY DURATION	14
5.7 CONCLUSION	15
6 BENEFIT-HARM ASSESSMENT	15
6.1 BACKGROUND	15
6.2 SAFETY	16
6.2.1 RISK MITIGATION STRATEGY -SAFETY	16
6.3 TOLERABILITY	16
6.3.1 LOCAL SIDE EFFECTS	16
6.3.2 SYSTEMIC SIDE EFFECTS	17
6.4 BENEFIT-HARM ASSESSMENT OF FREQUENT MAMMOGRAMS	18
6.5 POSSIBLE BENEFITS OF PARTICIPATION IN THE TRIAL	19

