5.3.1 Topical endoxifen - Phase 1 data

Atossa Genetics Inc., has performed two clinical endoxifen phase 1 studies, one with endoxifen as an oral compound and one with endoxifen as a topical compound. The topical phase 1 study is described in detail in the Investigators Brochure.

In the phase 1 topical endoxifen study, 25 healthy individuals received topical endoxifen at doses 0, 2, 6 and 10 mg/day. None of them experienced side-effects normally linked to tamoxifen, and thereby possibly endoxifen, exposure. There were no reports of hot flushes, vaginal discharge, mood swings, fatigue or breast pain/tenderness. These symptoms are associated with tamoxifen use and seen in more than 50% of the Karisma-2 participants. What was reported in the topical endoxifen phase 1 study was for tamoxifen atypical, non-dose dependent experiences of abnormal dreams, hypersomnia, vomiting and headache.

In the phase 1 topical endoxifen study, serum concentrations of endoxifen were low even for the highest dose group, 10 mg/day of daily topical endoxifen. Most measured samples were below or slightly above the limit of detection/quantitation. The mean concentration in the 10 mg group was 1.0 ng/mL and the maximum 5.0 ng/mL. Concentrations were too low to perform any pharmacokinetic analyses. Furthermore, there were no clinically significant safety signals (no measurable influence on coagulation system, liver function or sex hormone binding globulin) in any of the subjects receiving topical endoxifen.

In conclusion, topical endoxifen (at doses 0, 2, 6 and 10 mg/day) was well tolerated when administered daily for 28 days to 25 healthy volunteers. There were no dose-related or treatment-related trends in any of the safety and tolerability endpoints.

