6 BENEFIT-HARM ASSESSMENT

6.1 Background

In a broader sense, ethical considerations in clinical trials should focus on answering the question – does knowledge generated through the trial outweigh the possible harms inflicted on the participants? The most important task is to take the safety of study participants into consideration. Breast cancer incidence has increased rapidly over the last generations and currently one women per minute is diagnosed with breast cancer in Europe. It could therefore be argued that efforts taken to reduce the number of breast cancers are much needed. Tamoxifen has been used for adjuvant therapy for breast cancer for several decades and the side effects of tamoxifen are well-known. Side effects range from menopausal symptoms and mood swings to increased risks of endometrial cancer and thromboembolism. Tamoxifen has also been found to reduce the number of newly diagnosed cancers in perfectly healthy women but is not used to any larger extent due to the risk of bothersome as well as potentially very serious side-effects. Little is known about the side effects of endoxifen. Therefore, a conservative approach must be to assume that the toxicity of endoxifen is identical to that of

tamoxifen and that there is a dose dependency is used. The following sections discuss the potential risks associated with exposing healthy volunteers to topical endoxifen and the associated mitigation strategies. Possible benefits of participating in the trial are also described, as well as benefit-harm assessment of frequent mammograms.

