6.2 Safety

The most serious side effects of tamoxifen are thromboembolic events, endometrial cancer, sarcoma of the uterus and liver damage such as cirrhosis and steatosis. Markers of the coagulation system, liver function and levels of sex hormone binding globulin (SHBG) were therefore tested in the phase I topical endoxifen trial. Comparing levels before trial initiation and at 28 days of exposure to the study drug revealed no influence on these parameters, not even in the highest dose (10 mg) category. For more detailed information on the phase 1 results, please see Investigator Brochure.

During pregnancy, tamoxifen and its metabolites interact with rapidly growing and developing embryonic or foetal tissues. Tamoxifen exposure during pregnancy could lead to congenital malformations, spontaneous abortions and even foetal deaths.

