6.2.1 Risk mitigation strategy -Safety

The phase 1 data does not indicate a systemic influence on the systems but since it cannot entirely be ruled out that there is an effect on the coagulation system, liver function or SHBG, markers of their function will be measured at 3 and 6 months in this phase 2 study.

Patients with a previous cardiovascular event will be excluded from the study. Blood pressure will be measured before entering the study and women with a blood pressure $>140/90$ mm Hg will not be included in the trial. Possible signs of vaginal bleeding will be addressed immediately. Since only postmenopausal women will be included, pregnancy related safety issues are not a concern.

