10.5.3 Baseline (Month 0)

Meeting with Investigator

- The investigator will explain the nature and aim of the study, its procedures, possible side effects, requirements, restrictions and answer any questions.
- The study participant and the responsible investigator signs and dates the informed consent.
- A woman fulfilling the inclusion and exclusion criteria will be randomized to either placebo or any of two active substances.
- The woman will receive a sufficient amount of IMP for daily application for at least 3 months.
- Screening form, randomisation number and other study specific information will be filled in by investigator in the eCRF.

Procedures at baseline

After meeting with the investigator, the ICF is signed and randomization is performed, the following will be obtained:

- A total of 19.2 ml blood will be collected. 9.2 ml blood will be analysed for liver function tests, sex hormones and coagulation markers. 10 ml will be stored as a back-up sample for baseline measurements
- The participants will be asked to answer Karma CREME-1 baseline web-based questionnaire (see Study file; Questionnaires in Karma CREME-1)
- Measurement of weight and length
- Instructions are given on how to apply the topical endoxifen and what restrictions the participant shall adhere to (see Study file; Instruktioner Endoxifen kutan lösning)
- Instructions are given on how to report events and how to use the Karmapp

10.5.4 1 month after baseline (+2/-1 weeks)

- Karma CREME-1 follow up questionnaire including general symptoms, tamoxifen related symptoms, skin-related symptoms, compliance and health care contact connected to possible side effects

10.5.5 3 months after baseline (+/- 2 weeks)

- Mammogram (one image per breast only for density measurement purposes)
- A total of 19.2 ml blood will be collected. 9.2 ml blood will be analysed for liver function tests, sex hormones and coagulation markers. 10 ml will be used to measure for endoxifen markers
- The women will return empty sachets and secondary boxes for drug accountability. The women will receive a sufficient amount of IMP for daily application for at least 3 months
- Karma CREME-1 follow up questionnaire including general symptoms, tamoxifen related symptoms, skin-related symptoms, compliance and health care contact connected to possible side effects

10.5.6 6 months after baseline (+/- 2 weeks), visit at Karma Study Centre, end of study:

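### The synopsis bars any history of coagulopathy, but section 10.4 excludes only known APC-resistance, so a woman with another known thrombophilia who is event-free, mobile and not anticoagulated is eligible under one text and ineligible under the other.

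*Combined protocol and SAP*

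**What the plan says.** In the protocol synopsis, under diagnosis and main eligibility criteria, the rule is "No history of coagulopathies, cardio-vascular disorders and cancer". No subtype is named.

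Section 10.4 is the list that staff apply. Under its safety heading, the one disorder of haemostasis is "Known APC (Activated Protein C)-resistance, an inherited haemostatic disorder". Three other items concern thrombosis: previous thromboembolic disease, raised venous thrombosis risk caused by immobility, and regular prescribed anticoagulants in ATC group B01A.

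Section 10.5.3 then states: "A woman fulfilling the inclusion and exclusion criteria will be randomized to either placebo or any of two active substances".

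On risk, section 6.2 says "The most serious side effects of tamoxifen are thromboembolic events" and goes on to list others. Section 6.1 says that "a conservative approach must be to assume that the toxicity of endoxifen is identical to that of" tamoxifen, with dose dependency. Section 6.2.1 adds that "it cannot entirely be ruled out that there is an effect on the coagulation system". Section 10.7.10 explains the anticoagulant ban partly by saying "Prescription of anticoagulants indicates that person is at risk of thrombosis".

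**The concern.** The two texts give different answers for the same woman, and the broader safety promise is in the text that staff do not work from. Anyone who reads only the synopsis would believe that all coagulopathies are excluded.

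What is at stake is the safety of healthy volunteers. Section 10.4 already excludes APC-resistance without requiring a past event, and 10.7.10 treats thrombosis risk as a reason for exclusion. Neither reaches a woman with another known thrombophilia who has had no clot and takes no anticoagulant. The protocol gives no reason for treating her differently.

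The conflict can also surface after entry. Section 10.6 withdraws a participant who meets an exclusion criterion defined in the protocol, and it is unclear whether the synopsis line counts as one. Withdrawn women are not replaced.

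**Working it through.** **1. The two texts side by side.** The protocol gives no figure to reproduce here, so the first check is of wording. Take a woman with a known inherited or acquired thrombophilia other than APC-resistance, no thromboembolic event, normal mobility and no B01A drug.

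| Text | Result for her |
|---|---|
| Synopsis, main eligibility criteria | Barred |
| 10.3 Inclusion criteria | Nothing on clotting |
| 10.4, past thromboembolic disease | Not met |
| 10.4, APC-resistance | Not met |
| 10.4, immobility | Not met |
| 10.4 and 10.7.10, anticoagulants | Not met |
| 6.2.1 risk mitigation | Covers only past cardiovascular events and blood pressure |
| 10.5.2 pre-screening | Blood pressure, density, then the 10.3 and 10.4 lists |
| 10.5.3 | Randomised |

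**2. Could something else stop her before randomisation?** Section 10.4 has no exclusion at the investigator's discretion. The baseline coagulation sample is taken after randomisation (10.5.3), and no INR or aPTT limit is set for entry. The laboratory alerts (7.4, 11.4), discontinuation rules (10.6) and DSMB (12.3) act only after entry. One figure in 10.4 is missing from the text that I had; I assume that it adds no criterion.

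**3. How many women?** The documents give no prevalence. Assume that a proportion p of otherwise eligible women, between 0.1% and 1%, are in this position. Expected number = n × p, with 90 enrolled, 60 on active drug and 30 on 20 mg/day (synopsis, 10.7.5).

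| | p = 0.1% | p = 1% |
|---|---|---|
| Enrolled, n = 90 | 90 × 0.001 = 0.09 | 90 × 0.01 = 0.9 |
| Active drug, n = 60 | 60 × 0.001 = 0.06 | 60 × 0.01 = 0.6 |
| 20 mg/day, n = 30 | 30 × 0.001 = 0.03 | 30 × 0.01 = 0.3 |

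With a binomial count among 90, P(0) = (1 − p)^90, which is 0.914 at 0.1% and 0.405 at 1%. P(0 or 1) = (1 − p)^90 + 90p(1 − p)^89, which is 0.996 and 0.773. These are women enrolled or exposed, not women harmed.

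**4. How much systemic exposure?** Section 5.3.1 reports: "The mean concentration in the 10 mg group was 1.0 ng/mL and the maximum 5.0 ng/mL". Section 5.3.2 gives three ranges of endoxifen after oral tamoxifen. Comparing maximum with maximum:

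| Oral range (ng/mL) | 5.0 / oral maximum | Is 5.0 inside the range? |
|---|---|---|
| 11.4–44.8 | 5.0 / 44.8 = 11% | No, below it |
| 3.2–19 | 5.0 / 19 = 26% | Yes |
| 1.8–12.2 | 5.0 / 12.2 = 41% | Yes |

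Phase 1 tested at most 10 mg/day for 28 days. This trial gives one arm 20 mg/day for 6 months.

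**The case against.** The best defence is that a synopsis line is shorthand. Its cancer term has exceptions in 10.4, and its cardiovascular term becomes specific events plus a blood pressure limit. The coagulopathy term could likewise stand for the group of thrombosis items in 10.4, and naming APC-resistance alone could be deliberate. This stands in part: the documents do not prove which text is wrong, and narrowing the synopsis would also remove the contradiction. It does not settle the matter, because the protocol's own reasoning supports the broader rule for thrombophilia and no reason is given for the narrower one.

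The exposure argument also has force. Section 5.3.2 assumes systemic levels of roughly 5–10% of those after 20 mg oral tamoxifen. Most phase 1 samples were near or below the limit of detection or quantitation, and no effect on clotting was measured. This limits the risk. It does not remove it at a dose and duration that phase 1 did not cover.

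Three stronger readings are tempting, and the documents do not support them:

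- **That women with coagulopathies in general can be randomised.** Many are stopped by the event, immobility or anticoagulant items. The gap is the woman who meets none of these.
- **That bleeding disorders are an equal safety gap.** The risk cited is thrombosis. The bleeding concern in 10.7.10 relates to warfarin, which the anticoagulant ban already covers. Only the synopsis term itself points to bleeding disorders.
- **That topical exposure is comparable to oral exposure.** Dividing the phase 1 maximum by oral means gives larger ratios, but that is not like for like, and 5.0 ng/mL lies below one of the three oral ranges.

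**Conclusion.** The point holds, at minor severity. The synopsis and 10.4 disagree about a woman with a known thrombophilia other than APC-resistance who is event-free, mobile and not anticoagulated. Nothing before randomisation resolves the disagreement, and following 10.4 as written would enrol her. That conclusion rests on the text alone.

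Only the size rests on the assumed prevalence of 0.1% to 1%. On that assumption fewer than one such woman is expected among the 90, with two thirds of that number on active drug and one third on the dose not tested in phase 1. The primary endpoint, the sample size and the simulated operating characteristics in 9.1.3 are not affected.

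**What to change.** 1. In 10.4, replace the APC line with: *Known thrombophilia, inherited or acquired (including APC-resistance), with or without previous thrombosis.* Establish it by history at the investigator meeting, before randomisation.
2. Align the synopsis line with 10.4, so that both texts give the same rule.
3. Ask the sponsor whether the synopsis term was meant to cover bleeding disorders. Add them to 10.4 only if so.

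If the sponsor intends the narrower rule, the minimum is to narrow the synopsis and state why other known thrombophilias are acceptable.

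**Cost.** One history question at a meeting that 10.5.3 already schedules, with no new blood test, laboratory limit or delay. On the stated assumption, fewer than one candidate is lost per 90. The sample size stands, because 10.6 continues inclusion to 90 and a woman excluded at screening does not count towards it. The main burden is administrative: changing an exclusion criterion may be a substantial change under 12.6, which would need ethics committee and regulator approval.
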